5.3. Patient Enrollment

Enrollment will occur only after the patient has given written informed consent, all screening assessments have been completed, and the patient meets all eligibility criteria.

6. ADMINISTRATION OF NERATINIB AND LOPERAMIDE TREATMENTS

6.1. Neratinib

Neratinib will be supplied as 40-mg, film-coated tablets packaged in bottles with desiccant.

Neratinib (240 mg; provided as six 40-mg tablets) will be self-administered orally by patients on a daily basis, starting with Cycle 1/Day 1. Neratinib must be taken with food, preferably in the morning.

In patients with stage 1 to 3c disease, extended adjuvant treatment with neratinib will be given continuously as a single 28-day cycle followed by continuous daily dosing for up to 1 year

In patients with mBC, following completion of a 28-day cycle of neratinib monotherapy and completion of the second study colonoscopy procedure, neratinib will be given continuously in 21-day cycles in combination with capecitabine. On the day of the second study colonoscopy procedure in both groups, the morning dose of neratinib will be held. Neratinib will be resumed the day following the second study colonoscopy procedure. In both groups, daily dosing should continue until disease recurrence or progression (as determined by the Investigator), death, unacceptable toxicity, or other specified withdrawal criterion is met (see [Section 10](#)).

During the first 28 days, patients must use a diary to record their intake of neratinib (see [Section 8.5.2](#)).

6.1.1. Neratinib Dose Adjustment

Neratinib dose adjustment and/or discontinuation and/or management of toxicity should be performed according to [Appendix 2](#) and [Section 10.1](#).

Recommended dose reductions for the -1 and -2 dose levels of neratinib are listed in [Table 3](#).

Table 3: Dose Reduction Levels for Neratinib-Related Toxicity

Dose Level	Neratinib
Recommended Starting Dose	240 mg
First dose reduction	200 mg
Second dose reduction	160 mg
Third dose reduction	120 mg

mg = milligrams

If doses of neratinib are held, study procedures for that cycle will proceed on schedule as planned, without any delay. Missed dose(s) of neratinib (i.e., any dose that is not administered within the protocol-defined administration window) will not be made up. **Note: Patients should take one dose per calendar day.** The dose adjustment guidelines represent the minimum set of measures the Investigator must follow. However, additional measures may be taken, as necessary, for certain patients per the Investigator's medical judgment. All dose modifications/adjustments should be documented in the patient's source file.

Once the neratinib dose has been reduced for a patient, all subsequent cycles must be administered at that dose, unless further dose reduction is required. Dose re-escalation will only be permitted if explicitly approved in advance by the Sponsor. Evidence of this approval must be contained within the patient's source file.

Patients must discontinue the investigational product if a criterion for withdrawal is met (see [Section 10.1](#)).

Reintroduction of the discontinued investigational product at a later time during the active treatment phase is not permitted.

Detailed rules for dose adjustments of neratinib in case of toxicity, including the dose levels to which the investigational product should be adjusted, are provided in [Appendix 2](#).

6.2. Loperamide

Detailed dosing instructions and recommendations for management of diarrhea are provided in [Section 7.2](#). Prior to initiation of study drug in Cycle 1.

- Inform patients that they will experience diarrhea while taking neratinib.
- Loperamide should be taken as instructed
- The initial dose of loperamide 4 mg will be self-administered orally with the first dose of neratinib.
- During weeks 1-2 (day 1 – 14) of Cycle 1 loperamide 4 mg will be self-administered administered three time daily.
- During weeks 3-4 (days 15 – 28) of Cycle 1 loperamide 4 mg will be self-administered twice daily
- After the first 28 days, loperamide will be self-administered as needed (PRN) (not to exceed 16 mg per day).

Recommended loperamide dosing is listed below in [Table 4](#).

Table 4: Loperamide Dosing

Day	Loperamide Dose
1-14	Daily dose of 12 mg in 3 divided doses of 4 mg
15-28	Daily dose of 8 mg in 2 divided doses of 4 mg
29+	Daily dose as needed (not to exceed 16 mg per day)

During the first 28 days, patients must use a diary to record their intake of loperamide as well as the use of other antidiarrheals. Loperamide pill counts will be conducted only during the first cycle (28 days) of therapy.

Documentation of the number of stools at baseline should be captured in the patient's record. Any occurrences of loose stools, diarrhea or constipation must be documented by the patient and captured in the Patient Diary (see [Section 8.5.2](#)) during Cycle 1. The entries in the Patient Diary should be reviewed by the study staff together with the patient.

The Patient Diary will contain details of the daily number of unformed stools the patient has experienced since the last visit. Documenting the toxicity grade of the diarrhea or constipation by the study staff needs to be reported accurately on the Case Report Form (CRF) using the NCI CTCAE version 4.0 criteria.

Loperamide Dose Adjustment

Patients are expected to take loperamide prophylaxis as directed. However, patients may require individualization of loperamide prophylaxis dose (up to a maximum dose of 16 mg per day).

- For patients who develop diarrhea during Cycles 1, loperamide should be increased up to a maximum of 16 mg a day.
- If a patient is unable to tolerate loperamide due to symptomatic constipation, loperamide should be held until after the first bowel movement and then resumed at a dose reduced by one level.
- For recurrent symptomatic constipation events, hold loperamide until after the first bowel movement and then resume at a dose reduced to the next lower dose level.
- If a patient is unable to tolerate once-daily loperamide due to constipation, hold loperamide and discuss subsequent loperamide dosing with the Medical Monitor.
- Neratinib dosing should continue if loperamide is held.

Recommended dose reductions for loperamide are listed in [Table 5](#).

Table 5: Loperamide Dose Reduction Levels for Constipation

Dose Level	Loperamide Dose	Tablets/Capsules per Day
0	4 mg TID	6 tablets/capsules a day
-1	4 mg BID	4 tablets/capsules a day
-2	2 mg TID	3 tablets/capsules a day
-3	2 mg BID	2 tablets/capsules a day
-4	2 mg once a day	1 tablet/capsule a day

Abbreviations: BID = twice daily; mg = milligrams; TID = three times daily

If a patient experiences an AE leading to dose interruption of neratinib for reasons other than diarrhea, consider holding loperamide until neratinib treatment is resumed.

6.3. Capecitabine

Patients with mBC will receive capecitabine, beginning in Cycle 2 of treatment (i.e., following completion of the second study colonoscopy procedure and biopsy).

Capecitabine is available at 150 mg and 500 mg film-coated tablets.

Capecitabine (total dose of 1500 mg/m² daily, administered as 750 mg/m² in approximately evenly divided doses) will be self-administered orally by patients starting with Cycle 2/Day 1 (i.e. following completion of the second study colonoscopy procedure and biopsy). Doses are to

be taken daily on Days 1 to 14 of each 21-day cycle. Capecitabine should be taken with water within 30 minutes after a meal.

During treatment with neratinib plus capecitabine, patients should be monitored for conditions that may require dose to be held or discontinued as described in [Appendix 2](#). Careful attention should be paid to the onset of diarrhea or hand-foot syndrome in particular, and early dose adjustment or prophylactic therapy should be implemented as described in [Appendix 2](#).

Daily dose of neratinib plus capecitabine should continue until a criterion for treatment withdrawal or study withdrawal is met (see [Section 10.1](#) and [Section 10.2, respectively](#)).

Refer to the capecitabine (Xeloda®) [US Package Insert](#) and/or the [SPC](#) for further information on dosing, safety assessments and toxicity management.

6.3.1. Dose Adjustment

Investigational product dose adjustment and/or discontinuation should be performed according to [Appendix 2](#) and [Section 10.1](#).

Recommended dose reductions for the -1 and -2 dose levels of capecitabine in combination with neratinib are listed in [Table 6](#).

Table 6: Dose Reduction Levels for Capecitabine-Related Toxicity (When Administered in Combination with Neratinib)

Dose Level	Capecitabine (administered in combination with neratinib)
Starting Dose	1500 mg/m ² , 750 mg/m ² BID
-1 ^{aa}	1100 mg/m ² , 550 mg/m ² BID
-2 ^a	750 mg/m ² , 375 mg/m ² BID

Abbreviation: BID: twice daily

^a Since capecitabine is provided as 150 mg or 500 mg tablets, it is recommended that the capecitabine dose reduction(s) (to 75% [level -1] or 50% [level -2] of the starting dose) is rounded down to the nearest 500 mg or multiple of 150 mg for the BID dose. If the patient's body surface area is >2.0, the standard of care for the study center can be utilized for capecitabine mg/m² dosing.

6.4. Packaging, Labeling, and Storage

6.4.1. Neratinib

Neratinib will be supplied as 40-mg, film-coated tablets packaged in bottles with desiccant.

Neratinib should be stored at 25°C (77°F) or below; do not freeze. Neratinib should be stored with desiccant. Excursions are permitted from 15°C (59°F) to 30°C (86°F). Neratinib should be stored in a secure location with limited access. Patients should be instructed to store neratinib in a safe place at room temperature.

Detailed packaging information is available in the study reference manuals. Neratinib will be labeled according to local regulations and include the study number.

6.4.2. Loperamide

Commercially available loperamide will be provided to the subjects by the study sites.

6.4.3. Capecitabine

Commercially available capecitabine will be provided to the subjects with mBC by the study sites.

6.5. Drug Accountability and Treatment Compliance

The study site must maintain accurate records documenting dates and quantities of investigational product, capecitabine and loperamide supplied/ reimbursed by the Sponsor. Records must also be maintained documenting dates and quantities (i.e., pill counts) of neratinib, capecitabine and loperamide received, dispensed (per-patient), and returned (per-patient). Such documentation should permit a running log of the receipt and per-patient disposition of all investigational products on site. Any investigational product, capecitabine or loperamide accidentally or deliberately destroyed must also be documented.

Throughout the study, reconciliation will be made between the amounts of neratinib, capecitabine and loperamide supplied, dispensed, returned, and subsequently destroyed or returned to the Sponsor. All investigational products, capecitabine and loperamide will be returned to Sponsor or its representative, or destroyed at the site in accordance with local standard operating procedures, as specified in writing by the Sponsor.

Individual patient dosing compliance should be reviewed and documented at each study visit by study site staff. If patient non-compliance is noted, the patient should be re-instructed regarding proper dosing procedures in order to continue in the study. If repeated non-compliance is noted, additional steps may be taken, including withdrawal of the patient from the study (see [Section 10.2](#)).

7. CONCOMITANT MEDICATIONS

All concomitant medications and concomitant nonpharmacological treatments/therapies will be recorded at screening from 28 days prior to the signing of the informed consent form (ICF), on Day 1 of Cycle 1 through completion of the second study colonoscopy procedure. This will include the start date, stop date, generic name, route of administration, dose and indication for treatment. At screening, patients will be asked what medications they have taken during the previous 28 days and which medications are ongoing at the time of screening.

7.1. Permitted Concomitant Treatment

Any palliative and/or supportive care for cancer-related symptoms, which are not otherwise specified in the list of prohibited medications ([Section 7.3](#)), or drugs with potential for drug-drug interactions ([Section 7.4](#)), or in the associated Appendices ([Appendix 4](#), [Appendix 5](#), [Appendix 6](#)), including hormonal therapy (eg, tamoxifen, aromatase inhibitors) is permitted at the Investigator's discretion.

Specifically, the following treatments are permitted during the study:

- Standard therapies for preexisting medical conditions and for medical and/or surgical complications. All medication(s) as well as dose and length of therapy should be recorded in the case report form (CRF).
- Adjuvant endocrine therapy is allowed for hormone receptor-positive disease.
- Bisphosphonates and receptor activator of nuclear factor kappa-B ligand inhibitors (eg, denosumab), are allowed regardless of indication.
- Secondary prophylactic use of growth factors (e.g., granulocyte colony stimulating factor or granulocyte macrophage colony stimulating factor) may be implemented per the American Society of Clinical Oncology guidelines at the Investigator's discretion, if significant neutropenia or febrile neutropenia/infection is observed.

7.2. Required Loperamide Antidiarrheal Therapy

Diarrhea is the major dose-limiting toxicity of neratinib with onset typically occurring early in the course of treatment (during the first few weeks of treatment). Primary prophylactic use of antidiarrheal medication is **mandatory** for all enrolled patients taking neratinib.

As noted in [Section 6.2](#), loperamide is the recommended standard therapy to treat diarrhea in this study. If alternative antidiarrheal medication is proposed, this should be discussed with the Medical Monitor and the reason documented in the source documents. Second-line antidiarrheal treatments (diphenoxylate hydrochloride and atropine sulfate) may be used in Cycle 1. Adjunctive therapies (eg, octreotide [**SANDOSTATIN®**] (or equivalent as approved by the Sponsor) are also recommended for use when appropriate; however, the use of octreotide should be avoided in Cycle 1.

The Investigator must review with the patient the **Patient Instructions** for the management of diarrhea and the **Patient Diary** used by the patient to record daily the number of stools, use of loperamide and/or other anti-diarrheals, and the use of investigational product for the first cycle (28 days) of the study (see [Section 8.5.2](#)). Both the patient and the Investigator must sign the

patient instructions for the management of diarrhea. The Patient Instructions and Patient Diary are to be handed to the patient before leaving the site with investigational product on or before Cycle 1/Day 1, with clear instructions to contact the Investigator in the event of *de novo* onset or persistent Grade ≥ 2 diarrhea to discuss the appropriate course of treatment. The Investigator must also complete and sign the **Investigator Checklist** on or before Cycle 1/Day 1.

Documentation of any occurrences of loose stools or diarrhea must be as precise as possible and captured in the Patient Diary. For AE recording, documentation of “Intermittent” events of diarrhea is limited to Grade 1. If events of Grade 1 diarrhea are separated by 3 days without any diarrhea, then each event must be documented as separate AEs with corresponding start and stop dates.

The entries on the Patient Diary should be reviewed together with the patient. If the patient has experienced diarrhea since the last visit, details of the daily number of unformed stools provided on the diary help to grade the diarrhea as precisely as possible (per NCI CTCAE v.4.0). Also, the daily dose of loperamide (or other antidiarrheals, if applicable) noted on the diary will be reviewed and recorded on the CRF.

Loperamide (along with neratinib) will be dispensed directly by the site on or before Cycle 1/Day 1 and during subsequent visits as needed. It is very important to initiate treatment with loperamide concomitantly with the first dose of neratinib to minimize occurrence and severity of diarrhea.

Loperamide Prophylactic Dosing Instructions (Cycle 1)

- Inform patients that they will experience diarrhea while taking neratinib.
- Administer loperamide:
 - The initial dose of loperamide 4 mg will be self-administered orally with the first dose of neratinib.
 - For the first 14 days, loperamide 4 mg (2 tablets/capsules) will be self-administered orally by patients TID (total 12 mg a day).
 - During weeks 3-4 (days 15-28) loperamide 4 mg will be self-administered BID
 - After the first 28 days, loperamide will be self-administered as needed (PRN) (not to exceed 16 mg/day)
- For patients who develop diarrhea during Cycle 1, loperamide should be increased up to a maximum of 16 mg a day.
- At any time during the study, for patients with persistent Grade 1 diarrhea (<4 stools per day above baseline) on a maximum dose of loperamide (16 mg a day), Lomotil® (diphenoxylate hydrochloride and atropine sulfate) 1 tablet (2.5 mg) every 6 to 8 hours may be added (or equivalent as approved by Sponsor).
- For Grade 2 diarrhea during the 28 days of neratinib monotherapy following the second study colonoscopy procedure in patients with stage 1 to 3c breast cancer treated in the extended adjuvant setting, or during Cycle 2 in patients with mBC and beyond (4 to 6 stools per day above baseline, despite intensive anti-diarrheal therapy), consider adding octreotide (short-acting) 150 μ g subcutaneous [SC] injection TID, or after initial dose of

short-acting octreotide, if well tolerated, a single dose of octreotide LAR 20 mg by intramuscular (IM) injection (equivalent medication may be used with approval of the Sponsor).

- After resolution of diarrhea, loperamide prophylaxis can be increased in 2 mg increments with the goal of titrating to 1-2 bowel movements a day.
- Instruct patients to promptly report diarrhea symptoms.
- Instruct patient to record the number of stools per day and the dose of any anti-diarrheal medication taken each day (see [Section 8.5](#)).

For new onset uncomplicated Grade 1 or Grade 2 diarrhea

Dietetic measures

- Stop all lactose-containing products.
- Drink 8 to 10 large glasses of clear liquids per day (~2000 mL).
- Eat frequent small meals.
- Recommend low fat regimen enriched with bananas, rice, applesauce and toast until resolution of diarrhea.

Pharmacological treatment

- Administer loperamide: initial dose of 4 mg (2 tablets/capsules) with the first bout of diarrhea followed by 2 mg (1 tablet/capsule) every 4 hours or after every unformed stool (maximum 16 mg a day) and continue loperamide at this frequency until diarrhea-free for 12 hours.
- At any time during the study, for patients with persistent Grade 1 diarrhea on loperamide, Lomotil® (diphenoxylate hydrochloride and atropine sulfate) 1 tablet (2.5 mg) every 6 hours to 8 hours may be added (or equivalent as approved by the Sponsor).
- For 28 days of neratinib monotherapy following the second study colonoscopy procedure in patients with stage 1 to 3c breast cancer treated in the extended adjuvant setting, or during Cycle 2 in patients with mBC and beyond, for Grade 2 diarrhea (4 to 6 stools per day above baseline, despite intensive antidiarrheal therapy), consider adding octreotide (short-acting) 150 µg subcutaneously (SC) TID; or after initial dose of short-acting octreotide, if well tolerated, a single dose of octreotide LAR 20 mg intramuscularly (IM) (equivalent medication may be used with approval of the Sponsor).

For Grade 3 or Grade 4 diarrhea with complicating features (dehydration, fever, and/or Grade 3-4 neutropenia)

Dietetic measures (same as above)

Pharmacologic treatment

- Administer loperamide: initial dose of 4 mg (2 tablets/capsules) with the first bout of diarrhea followed by 2 mg (1 tablet/capsule) every 4 hours or after every unformed stool (maximum 16 mg a day) and continue loperamide at this frequency until diarrhea-free for

12 hours. Then titrate the amount of loperamide used to keep diarrhea controlled (<4 stools/day).

- Administer octreotide [100-150 µg SC BID or intravenously (IV) (25-50 µg/h) if dehydration is severe, with dose escalation up to 500 µg SC TID].
- Use IV fluids as appropriate.
- Consider prophylactic antibiotics as needed (eg, fluoroquinolones) especially if diarrhea is persistent beyond 24 hours or there is fever or Grade 3-4 neutropenia.

The Investigator or designee should contact the Sponsor or the Medical Monitor for advice if at any time there is a concern for the appropriate course of action for the management of diarrhea.

Stool cultures should be done to exclude infectious causes of Grade 3 or Grade 4 diarrhea or diarrhea of any grade with complicating features (dehydration, fever, and/or Grade 3 or Grade 4 neutropenia) per the Investigator's discretion. Results from occult blood, fecal leukocyte stain, *Clostridium difficile*, *Campylobacter*, *Salmonella*, and *Shigella* testing, when performed, should be reported using the appropriate CRF.

Patients with significant diarrhea who are unresponsive to medical treatment may require treatment interruption or dose reduction.

7.3. Prohibited Concomitant Treatment

The following treatments are prohibited throughout the duration of the active (treatment) stage/phase of the study:

- Any concurrent chemotherapy, radiotherapy (including palliative radiotherapy), surgery related to cancer, anticancer immunotherapy, or other anticancer treatments, except hormonal therapy (eg, tamoxifen, aromatase inhibitors), including other investigational agents.
- Acarbose, aspirin, proton pump inhibitors, NSAIDs, histamine H2-receptor antagonists, selective serotonin inhibitors, and ticlopidine (See Section 5.2 Exclusion Criterion 2) are excluded in Cycle 1 and until after the completion of the second study colonoscopy procedure.
- Systemic steroid use, by oral or parenteral route, including budesonide in Cycle 1 until after the completion of the second study colonoscopy procedure.

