2.4. Study Rationale

A rat model for neratinib-associated diarrhea has identified inflammation of the terminal ileum and proximal colon as a potential cause of the neratinib-related diarrhea. Studies conducted in this model demonstrated that budesonide, a locally acting corticosteroid used for inflammatory GI conditions, and coleselam, a bile acid sequestrant, each reduced the amount of days with moderate diarrhea compared with neratinib alone. In the proximal colon, rats treated with neratinib had higher levels of apoptosis compared with controls; budesonide significantly reduced histopathological injury in the proximal and distal colon in rats (Secombe et al, 2017; Secombe et al, 2019).

Microscopic colitis (MC) is a relatively common cause of chronic watery diarrhea. The diagnosis is based upon characteristic histological findings in the presence of diarrhea. The symptoms of MC are non-specific, and many patients meet the diagnostic criteria for irritable bowel syndrome; therefore, colon biopsies are required to definitively distinguish MC from the much more common irritable bowel syndrome.

MC has two main subtypes, lymphocytic colitis and collagenous colitis, with the main distinction being histological. The characteristic biopsy finding in lymphocytic colitis is intraepithelial lymphocytosis, defined as >20 intraepithelial lymphocytes per 100 surface epithelial cells. In addition, the lamina propria contains a mixed infiltrate of acute and chronic inflammatory cells. Collagenous colitis has similar inflammatory findings, although the intraepithelial lymphocyte infiltrate tends to be less prominent. The distinguishing histological feature of collagenous colitis is a thickened subepithelial collagen band (>7 μ m, compared with normal of $\leq 5 \mu$ m). Despite the normal appearance grossly, biopsies often show surface epithelial damage.

The ideal location in the colon to obtain biopsies is not clear. The inflammation and collagen thickening are not always uniform throughout the colon, and inflammation in lymphocytic colitis and collagen thickening in collagenous colitis may be worse in the right versus left colon. It is

well established that distal colon biopsies are not sufficiently sensitive to make the diagnosis and that proximal and distal biopsies are standard of care.

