4. INVESTIGATIONAL PLAN

4.1. Overall Study Design

This is an open-label, phase 2 study that will investigate colon pathology in patients with HER2-positive breast cancer treated with neratinib as monotherapy.

All patients will receive neratinib for the first 28 days as a single daily dose of 240mg.

Following the second study colonoscopy procedure:

- For patients being treated for stage 1 to 3c breast cancer in the extended adjuvant setting, neratinib will continue to be administered at a single daily dose of 240mg until completion of one year of therapy from start of treatment, or until disease recurrence (as determined by the Investigator), death, unacceptable toxicity, or other specified withdrawal criterion.
- For patients being treated for metastatic breast cancer (mBC), capecitabine will be introduced after the second study colonoscopy procedure at a dose of 750mg/m² twice daily for 14 days of each 21 day treatment cycle, with neratinib administered continuously throughout at 240mg daily, until disease progression, death, unacceptable toxicity, or other specified withdrawal criterion.

All patients will receive loperamide diarrhea prophylaxis daily for one (1) 28-day cycle and then as needed.

Following a 28-day screening period ([Section 9.1](#)), eligible patients will be enrolled. Baseline assessments will be performed prior to Cycle 1/Day 1 dosing. Patients will then participate in the active treatment phase, consisting of, in both groups, a single 28-day cycle of neratinib monotherapy ([Section 9.2](#)). Neratinib and loperamide will be administered orally by patients as described in [Section 6](#). The morning dose of neratinib will be held on the day of the second study colonoscopy procedure ([Section 6.1](#)).

Colonoscopy will be performed after eligibility has been confirmed, but prior to administration of the first dose of neratinib on Day 1 of Cycle 1, and at Day 30 (\pm 3 days). Thereafter, extended adjuvant patients with stage 1 to 3c breast cancer will continue to receive neratinib monotherapy for 1 year or until progression of disease, death, or intolerance to study prescribed therapy. Patients with mBC will continue to receive neratinib in 21-day cycles, beginning in Cycle 2, after completion of the second study colonoscopy procedure, in combination with capecitabine administered on Day 1-14 of each cycle, until progression of disease, death, or intolerance to study prescribed therapy.

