5.2. Exclusion Criteria

A patient will be excluded from this study if she/he meets any of the following criteria.

1. Patients with confirmed stage 1 through stage 3c breast cancer currently receiving chemotherapy, radiation therapy, immunotherapy, or biotherapy for breast cancer.
2. Patients with mBC that have received prior capecitabine or HER2 directed TKI therapy.
3. Currently using drugs that have been implicated as causing microscopic colitis/watery diarrhea, such as acarbose, aspirin, proton pump inhibitors, nonsteroidal anti-inflammatory drugs (NSAIDs), histamine H₂-receptor antagonists, selective serotonin reuptake inhibitors, and ticlopidine ([Pardi, 2017](#)).
4. Major surgery within <28 days of starting treatment or received chemotherapy, investigational agents, or other cancer therapy, except hormonal therapy (eg, tamoxifen, aromatase inhibitors), <14 days prior to the initiation of investigational products.
5. Active uncontrolled cardiac disease, including cardiomyopathy, congestive heart failure (New York Heart Association functional classification of ≥ 2 ; including individuals who currently use digitalis, beta-blockers, or calcium channel blockers specifically for congestive heart failure), unstable angina, myocardial infarction within 12 months of enrollment, or ventricular arrhythmia.
6. QTc interval >0.450 seconds (males) or >0.470 (females), or known history of QTc prolongation or Torsade de Pointes (TdP).
7. Diagnosis of inflammatory bowel disease.
8. Screening laboratory assessments outside the following limits:

Laboratory Parameters	Required Limit for Exclusion
Absolute neutrophil count (ANC)	$\leq 1,000/\mu\text{l}$ ($\leq 1.0 \times 10^9/\text{L}$)
Platelet count	$\leq 50,000/\mu\text{l}$ ($\leq 100 \times 10^9/\text{L}$)
Hemoglobin	$\leq 8 \text{ g/dL}$ (transfusions allowed) Transfusions must be at least 14 days prior to initiation of treatment
Total bilirubin	$>1.5 \times$ institutional upper limit of normal (ULN) (in case of known Gilbert's syndrome, $<2 \times$ ULN is allowed)
Aspartate aminotransferase (AST) and/or alanine aminotransferase (ALT)	$>2.5 \times$ institutional ULN ($>5 \times$ ULN if liver metastases are present in mBC patients)
Creatinine	Creatinine clearance $<30 \text{ mL/min}$ (as calculated by Cockcroft-Gault formula ^a or Modification of Diet in Renal Disease [MDRD] formula ^b)
International Normalized Ratio (INR)	≥ 1.5

^a [Cockcroft and Gault, 1976](#)

^b [Levey et al, 1999](#)

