9. Active, unresolved infections.
10. Patients with a second malignancy, other than adequately treated non-melanoma skin cancers, in situ melanoma or in situ cervical cancer. Patients with other non-mammary malignancies must have been disease-free for at least 5 years.

11. Currently pregnant or breast-feeding.
12. Significant chronic gastrointestinal disorder with diarrhea as a major symptom (eg, Crohn's disease, malabsorption, or Grade ≥ 2 National Cancer Institute [NCI] Common Terminology Criteria for Adverse Events Version 4.0 [CTCAE v.4.0] diarrhea of any etiology at baseline).
13. Clinically active infection with hepatitis B or hepatitis C virus.
14. Evidence of significant medical illness, abnormal laboratory finding, or psychiatric illness/social situations that could, in the Investigator's judgment, make the patient inappropriate for this study.
15. Known hypersensitivity to any component of the investigational products; known allergies to any of the medications or components of medications used in the trial.
16. Unable or unwilling to swallow tablets.

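### Steroids and budesonide are restricted before the second biopsy but not at or before the baseline biopsy, so the primary change from baseline could compare two biopsies taken under different steroid conditions

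*Protocol*

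**What the plan says.** Protocol Section 7.3 opens its list with "The following treatments are prohibited throughout the duration of the active (treatment) stage/phase of the study". One item on that list is "Systemic steroid use, by oral or parenteral route, including budesonide in Cycle 1 until after the completion of the second study colonoscopy procedure".

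The baseline colonoscopy comes after eligibility is confirmed and "prior to administration of the first dose of neratinib on Day 1 of Cycle 1" (Section 4.1). Section 9.1 lists it among the screening and baseline activities. Both schedules in Appendix 1 instead mark it in the C1/D1 column, whose visit window reaches back 3 days.

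For another group of drugs the protocol has a rule at entry. Exclusion criterion 3 in Section 5.2 removes patients who are "Currently using drugs that have been implicated as causing microscopic colitis/watery diarrhea, such as acarbose, aspirin, proton pump inhibitors" and others, including NSAIDs and SSRIs. Section 7.3 bars the same group from Cycle 1 until the second colonoscopy is done. None of the 16 exclusion criteria names steroids or budesonide.

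The rationale in Section 2.4 reports that "budesonide significantly reduced histopathological injury in the proximal and distal colon in rats". On medication history, Section 7 says: "At screening, patients will be asked what medications they have taken during the previous 28 days".

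**The concern.** The primary endpoint (Section 12.3.1) is a within-patient change between two sets of biopsies. The secondary marker endpoint (Section 12.3.2) is a change between the same two time points. Such a change can be read as a drug effect only if other influences on the colon and on the markers are alike on both occasions. By barring steroids before the second colonoscopy, the plan treats them as something that should not be present when tissue is taken. It does not do the same for the first.

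A patient could follow every rule and still give a baseline set under steroid and a second set without it. The study is non-randomized and open-label with no comparator (Section 4.3), so nothing in the data would separate a lifted steroid effect from a neratinib effect.

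**Working it through.** The plan gives no figure on this point, and its sample size rests on feasibility (Section 12.5). The main check is therefore a comparison of texts.

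**Step 1. Which rule applies at which biopsy?**

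| Drug group | At or before baseline colonoscopy | Cycle 1 to second colonoscopy |
|---|---|---|
| NSAIDs, PPIs, SSRIs and similar | Exclusion criterion 3 | Section 7.3 |
| Systemic steroids, budesonide | No rule found | Section 7.3 |

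**Step 2. Does any other rule fill the empty cell?**

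- Section 7.4 advises against strong CYP3A4 inducers, and Appendix 4 lists dexamethasone and prednisone as inducers. That advice also covers only the active phase.
- The schedule footnotes withhold oral medication on the day of colonoscopy. That is one day, and oral drugs only.
- If the baseline colonoscopy falls on Day 1 or in its 3-day window, Section 7.3 might be read to include it. Use up to the day before would still be allowed.

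The cell stays empty.

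**Step 3. Which way could the error go?** Let *L* be inflammation present before neratinib, *s* the part of it masked by steroid at baseline (0 ≤ *s* ≤ *L*), and *d* the change due to neratinib. Assume the masking has gone by the second biopsy.

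- Baseline reading = *L* − *s*
- Second reading = *L* + *d*
- Observed change = (*L* + *d*) − (*L* − *s*) = *d* + *s*

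The observed change exceeds the neratinib effect by *s*. If there was no inflammation to mask (*L* = 0), then *s* = 0 and there is no error. The problem therefore needs both steroid use at baseline and pre-existing inflammation.

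**Step 4. How much of the data is one patient?** 1/5 = 20%; 1/3 = 33%.

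**Step 5. How likely is at least one exposed patient?** The documents give no frequency of steroid use at baseline. For scale only, let *p* be an assumed frequency. The chance of at least one exposed patient is 1 − (1 − *p*)^*n*:

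| Assumed *p* | *n* = 3 | *n* = 5 |
|---|---|---|
| 2% | 5.9% | 9.6% |
| 5% | 14.3% | 22.6% |
| 10% | 27.1% | 41.0% |
| 20% | 48.8% | 67.2% |

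For example, 1 − 0.95³ = 0.143. These are chances of exposure. The chance of a misleading pair is lower, because step 3 also requires inflammation to mask.

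**Step 6. Would a later rule catch it?** Section 10.4 replaces only patients without two colonoscopies with successful biopsies, so an exposed pair stays in. SAP Section 6.8 lists concomitant medications, but neither document says how steroid use enters the reading of paired pathology. SAP Section 2.1.1 leaves the primary objective outside the SAP.

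**The case against.** The best case against the point has four parts.

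- **Masked inflammation is already made unlikely.** Exclusion 7 removes patients with "Diagnosis of inflammatory bowel disease". Exclusion 12 removes "Significant chronic gastrointestinal disorder with diarrhea as a major symptom" and also Grade 2 or higher diarrhea at baseline. Exclusion 14 lets the investigator decline an unsuitable patient. This stands and lowers the likelihood. It does not close the gap: exclusions 7 and 12 do not address steroids taken for non-bowel reasons, and exclusion 14 is a judgment, not a rule.
- **The interval is short.** On the Appendix 1 schedules the baseline colonoscopy is at most 3 days before Day 1, so the patient must be on a steroid then and off it almost at once. This stands for those schedules. Section 9.1 can be read to allow an earlier date within screening, and use before the colonoscopy is unrestricted on either reading.
- **The evidence is indirect.** The budesonide result comes from rats given neratinib, whereas the baseline biopsy precedes neratinib. This stands. A reader might infer that inflammation after steroid withdrawal will appear and pass for a neratinib effect. The documents describe no such withdrawal effect and support only the possibility of masking in step 3.
- **An exposed patient would be visible.** Medication is recorded from 28 days before consent, and listings and narratives are the main presentation. This stands as to visibility, but nothing requires the exposure to be considered when the pair is interpreted.

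Two further inferences should be resisted. A reader might say Sections 5.2 and 7.3 contradict each other. They do not: a prohibited list may be wider than an exclusion list, and a patient who must stay on a steroid simply cannot comply with 7.3. A reader might also object that criterion 3 covers only current use and has no look-back. The documents say nothing about how long those drugs' effects last, so that adds no weight here.

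**Conclusion.** The point holds as a gap in the control of conditions at baseline. Steroids and budesonide are restricted for the second biopsy only, while another group of colon-relevant drugs is restricted for both. A plan followed exactly can therefore give a primary pair, and paired ESR, CRP and fecal markers, taken under different steroid conditions.

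If that happens in a patient with inflammation to mask, the change is overstated, and that patient is 20% to 33% of the primary data. This assumes the masking has gone by the second biopsy. How often it would happen cannot be derived from the documents, and the exclusions make it less likely. The gap does not show that the results will be biased. It is worth closing because the correction is small and no control arm could reveal the error afterwards.

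**What to change.** 1. Reconcile Section 5.2 and the synopsis with Section 7.3 so that the steroid and budesonide restriction applies equally to both biopsies. Make it a separate eligibility line. It does not belong in criterion 3, which covers drugs implicated as causing colitis or watery diarrhea. No patient should be asked to stop a treatment for this purpose, and no washout length is proposed here.
2. From the 28-day medication history already collected, state any steroid or budesonide exposure before the baseline colonoscopy beside each patient's paired pathology and marker results. Put this in the pathology report or the patient narrative, since the SAP does not address the primary objective and plans no pathology listing.

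The cost is one line in the eligibility criteria and one entry per patient in the report, with no new data collection. The downside is that a patient on a steroid at entry becomes ineligible, although one who must stay on it could not comply with Section 7.3 anyway.
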